### 8.2.2 Imiquimod

Imiquimod is a topical immune response modifier and a 5% formulation has been approved for the treatment of AKs in the US and Europe (Aldara® cream) with a different dosage regimen. The dose regimen in Europe is one application 3 days per week for 4 weeks, with a 4-week treatment pause followed, if necessary, by another 4-week treatment period. The dose regimen in the US is two applications per week for 16 weeks. In this trial, subjects in the imiquimod group will be treated according to the EU dosage regimen.

Imiquimod is an immune response modifier. In animal models imiquimod has been shown to stimulate the immune system by activating antigen-presenting cells such as monocytes/

---

macrophages and dendritic cells to produce interferon and other cytokines and chemokines, which leads to the stimulation of the adaptive immune response.

The safety and efficacy of imiquimod applied 3 times per week for one or two courses of 4 weeks, separated by a 4-week treatment-free period has been demonstrated in two double-blind vehicle controlled clinical trials , (see more information in the SmPC of Aldara®, [Appendix V](#)).

The rate of progression to SCC was reported to be 1.6% (2/128 patients) within one year. There are no data on recurrence and progression rates beyond 1 year ([Appendix V](#)).

### 8.3 TRIAL RATIONALE

The purpose of this trial is to evaluate the risk of SCC after the treatment with ingenol mebutate gel. Imiquimod has been chosen for comparison as the treatment that is most comparable marketed field treatment with regard to efficacy. The cumulative incidence of SCC in a cohort of subjects with multiple AKs on the face or scalp who have been treated with ingenol mebutate gel or imiquimod cream will be evaluated.

To ensure accurate diagnosis a biopsy of a representative lesion will be taken to confirm AK prior to randomisation. Further, the biopsy is expected to identify a number of subjects who have SCC at screening and are therefore not eligible for the trial. In order to increase the likelihood of detecting an increased risk, if any, the subjects in both groups will be treated for 2 cycles if complete clearance is not obtained at Week 8. To obtain a reasonable number of SCC cases, subjects will be followed for 3 years and will be assessed for SCC (and other neoplasias) in the treatment area at regular intervals.

The overall design will be a two-arm trial where patients are initially all treated with one cycle of either ingenol mebutate gel or imiquimod cream according to the normal treatment schedule for face and scalp. Subjects in the imiquimod group will be treated according to the approved EU dosage regimen. After 8 weeks, patients who are completely cleared of all AKs in the selected treatment area will continue further observation in the Follow-up period, whereas those who are not cleared will be retreated with a second treatment cycle. For the purpose of this trial the minimum period between the two treatment cycles, i.e. the period between the initial treatment cycle and possible retreatment, will be 8 weeks which is the time

---

when the treatment response would be evaluated in clinical practice for both products. Adverse events, LSRs and efficacy will also be compared between the two treatments.

Since AK is a chronic disease and neither imiquimod nor ingenol mebutate are universally effective, need may arise in some subjects after the randomised treatment period for other treatment(s) in the selected treatment area than the intervention stipulated by the protocol. In such cases the choice should be to repeat the initial treatment (imiquimod or ingenol mebutate) as previously given to the subject (cross-over between imiquimod and ingenol mebutate is not allowed) or apply lesion-based cryotherapy. In order to avoid confounding of the results, other treatments will be avoided for as long as medically permissible.

## **9 TRIAL OBJECTIVES**

### **9.1 PRIMARY OBJECTIVE**

To compare the cumulative incidence of SCC after treatment with ingenol mebutate gel and imiquimod cream.

The primary response criterion is diagnosis of SCC (defined as invasive SCC i.e. excludes SCC in situ) in the treatment field across the 3-year trial period.

### **9.2 SECONDARY OBJECTIVES**

To compare the cumulative incidence of neoplasia and the short-term and 12-month efficacy of ingenol mebutate gel with imiquimod cream.

The secondary response criteria are:

1. Diagnosis of SCC and other neoplasia in the treatment field over a 3-year period.
2. Complete clearance after the last treatment cycle (at Week 8 or 16)
3. Partial (at least 75%) clearance after the last treatment cycle (at Week 8 or 16)
4. Complete clearance at 12 months, defined as no AKs in the selected treatment area at any time from the last treatment cycle at Week 8 or 16 through to Month 12.

---

## 10 INVESTIGATIONAL PLAN

### 10.1 TRIAL DESIGN

#### 10.1.1 Overall Design

This is a phase 4, multi-centre, randomised, two-arm, open label, active-controlled, parallel group, 36-month trial.

All subjects who qualify for this trial are to have 5 to 9 clinically typical, visible and discrete AK lesions (confirmed by histopathology of one of the AKs prior to randomisation) within a contiguous 25 cm^2 treatment area on the face or scalp. This area of skin will be referred to as the selected treatment area.

In case of baldness or partial baldness, the forehead should be defined by the previous hairline.

Subjects will be randomised in a 1:1 ratio to the following treatment arms:

- Arm A: Ingenol mebutate gel 0.015% applied daily for 3 consecutive days to the selected treatment area followed by 8 weeks' rest. Retreatment for another 3 consecutive days if the treatment field is not completely cleared of AKs at Week 8
- Arm B: Imiquimod 5% cream applied 3 days per week for 4 weeks to the selected treatment area followed by 4 weeks' rest. Retreatment for 4 weeks if the treatment field is not completely cleared of AKs at Week 8.

Study visits will take place at Screening (Visit 1), during the treatment period on Days 1 and 4, Weeks 2, 4 and 8 (Visits 2 to 6) for initial treatment and, if retreatment is required, on Week 8+3 days and Weeks 10, 12, and 16 (Visits 7 to 10). During the Follow-up period visits will take place at Week 20 and Months 12, 18, 24, 30 and 36 (Visits 11 to 16).

#### 10.1.2 Individual Phases

At the Screening (Visit 1) subjects will sign the study-specific consent form in the presence of the investigator and subject's eligibility will be checked and the selected treatment area will be identified. A biopsy will be taken of one AK lesion in the selected treatment area for histological confirmation of AK.

---

**Treatment Period (Day 1 to Week 16)**

At Day 1 (Visit 2), the subject eligibility will be confirmed and subjects will be randomised to treatment with either ingenol mebutate gel or imiquimod cream. The selected treatment area will be marked on the skin and the first dose will be applied under the supervision and management of the trial personnel. Subsequent doses will be applied at home.

At the next visits (Day 4 and Weeks 2 and 4; Visits 3 to 5) a clinical assessment of the selected treatment area will be performed. The selected treatment area will be assessed for local skin responses (LSRs) and any adverse events (AEs). If there is suspicion of SCC, BCC, or other neoplasia when clinical assessment is performed, a biopsy will be taken and trial treatment will be stopped but the subject will remain in the trial. At Week 8 (Visit 6), a clinical assessment of the selected treatment area will be performed as for previous visits. An AK count in the selected treatment area will also be conducted.

At Week 8, subjects who are completely cleared in the selected treatment area will continue into the Follow-up Period. Subjects, who are not completely cleared in the selected treatment area will have a second treatment cycle and will attend visits at Week 8+3 days and Weeks 10, 12, and 16 (Visits 7 to 10). The assessments will be the same as during the first treatment cycle. After the second treatment cycle subjects will enter the Follow-up Period.

Until the Follow-up period (Week 20), no other treatments and procedures are allowed in, and within 5 cm of the selected treatment area. Outside the selected treatment area (up to within 5 cm), procedures such as cryotherapy will be allowed; field therapy will not be allowed.

**Follow-up Period (Week 16 to Month 36).**

Visits will be performed at Week 20 and Months 12, 18, 24, 30 and 36 (Visits 11 to 16), at which a clinical assessment of neoplasia in the selected treatment area will be performed. If there is suspicion of SCC, BCC, or other neoplasia when clinical assessment is performed, a biopsy will be taken. An AK count in the selected treatment area will be conducted.

From Week 20 until Month 36 procedures such as cryotherapy will be allowed in, and within 5 cm of the selected treatment area. Further, at the discretion of the Investigator and according to nationally available product and treatment guidelines, the same treatment as originally administered is allowed (imiquimod or ingenol mebutate). Cross-over between imiquimod

and ingenol mebutate is not allowed. Investigators will be encouraged to pursue these treatment options where clinically relevant before employing other treatments.

Outside the selected treatment area (up to within 5 cm) all treatments will be allowed, although investigators will be encouraged to avoid cross-over between imiquimod and ingenol mebutate.

### **10.1.3 Individual Visits**

#### Screening (Visit 1, -42 to -14 days)

Eligibility will be checked according to the inclusion and exclusion criteria and the subject will sign the study-specific consent form in the presence of the investigator or his/her designee prior to any screening procedures taking place.

The following information will be recorded:

- Date of birth, sex, race, ethnic origin (self-report), height, weight, Fitzpatrick skin type, relevant medical/surgical history, concurrent diagnoses, concomitant medication, AK and SCC treatment history.
- Abbreviated physical examination including general appearance, regional lymph nodes and dermatologic examination of the skin in general.
- Vital signs (resting blood pressure and heart rate) and oral or ear temperature.

The selected treatment area will be identified by the dermatologist and documented on the study transparency using a three-point landmark technique. Detailed instructions for the three-point landmark technique are given in [Appendix IV](#).

A biopsy will be taken of one AK lesion in the selected treatment area (see [10.7.4](#)) for histological confirmation of AK.

Female subjects of childbearing potential will have a urine pregnancy test.

#### Visit 2 (Day 1)

Subject eligibility will be checked according to the inclusion and exclusion criteria. Once eligibility is confirmed, assessment of the selected treatment area, including LSRs and AK lesion count will be performed.

---

The subjects will be randomised to treatment with either ingenol mebutate gel or imiquimod cream. A trial medication kit will be assigned through an Interactive Web Response (IWR) System. The selected treatment area will be marked on the skin and the first dose of study medication will be applied under the supervision and management of the trial personnel (the subsequent doses will be applied at home).

Visit 3 (Preferred on Day 4, with a visit window of +2 days)

Visit 3 will include:

- Clinical assessment of neoplasia in the selected treatment area (biopsy if there is suspicion of SCC, BCC or other neoplasia)
- Dermatologic examination of the selected treatment area(s) including LSRs
- Reporting of (S)AEs (see [Table 2](#))
- Reporting of concomitant medication, treatments and procedures
- Return of trial medication (only for subjects treated with ingenol mebutate)
- Trial medication compliance

Visit 4 (Week 2, Day 15 ± 2 days)

Visit 4 will include:

- Clinical assessment of neoplasia in the selected treatment area (biopsy if there is suspicion of SCC, BCC or other neoplasia)
- Dermatologic examination of treated selected treatment area(s) including LSRs
- Reporting of (S)AEs (see [Table 2](#))
- Reporting of concomitant medication, treatments and procedures
- Trial medication compliance (for subjects treated with imiquimod)

Visit 5 (Week 4, Day 29 ± 3 days)

Visit 5 will include:

- Clinical assessment of neoplasia in the selected treatment area (biopsy if there is suspicion of SCC, BCC or other neoplasia)
- Dermatologic examination of the selected treatment area(s) including LSRs
- Reporting of (S)AEs (see [Table 2](#))
- Reporting of concomitant medication, treatments and procedures
- Return of trial medication and trial medication compliance (for subjects treated with imiquimod)

---

Visit 6 (Week 8, Day 57 ± 3 days)

Visit 6 will include:

- Clinical assessment of neoplasia in the selected treatment area (biopsy if there is suspicion of SCC, BCC or other neoplasia)
- Dermatologic examination of the selected treatment area including LSRs and AK count.
- Reporting of (S)AEs (see [Table 2](#))
- Reporting of concomitant medication, treatments and procedures
- Urine pregnancy test for female subjects of childbearing potential
- An abbreviated physical examination

Subjects who are not completely cleared in the selected treatment area will be retreated with a Second Treatment Cycle (Visits 7 to 16). At this visit the first dose of study medication will be applied under the supervision and management of the trial personnel (the subsequent doses will be applied at home).

Subjects, who are completely cleared in the selected treatment area (an AK count of zero), will continue in the Follow-up Period until trial completion at Month 36 (Visits 11 to 14).

Visit 7 – Only if Retreatment is required (3 days after Visit 6 with a visit window of +2 days)

Visit 7 will include:

- Clinical assessment of neoplasia in the selected treatment area (biopsy if there is suspicion of SCC, BCC or other neoplasia)
- Dermatologic examination of the selected treatment area(s) including LSRs
- Reporting of (S)AEs (see [Table 2](#))
- Reporting of concomitant medication, treatments and procedures
- Return of trial medication (for subjects treated with ingenol mebutate)
- Trial medication compliance

Visit 8 – Only if Retreatment is required (Week 10, 14 days ± 2 days after Visit 6)

Visit will include:

- Clinical assessment of neoplasia in the selected treatment area (biopsy if there is suspicion of SCC, BCC or other neoplasia)
- Dermatologic examination of the selected treatment area(s) including LSRs

- 
- Reporting of (S)AEs (see [Table 2](#))
  - Reporting of concomitant medication, treatments and procedures
  - Trial medication compliance (for subjects treated with imiquimod)

Visit 9 – Only if Retreatment is required (Week 12, 28 days  $\pm$  3 days after Visit 6)

Visit 9 will include:

- Clinical assessment of neoplasia in the selected treatment area (biopsy if there is suspicion of SCC, BCC or other neoplasia)
- Dermatologic examination of the selected treatment area(s) including LSRs
- Reporting of (S)AEs (see [Table 2](#))
- Reporting of concomitant medication, treatments and procedures
- Return of trial medication and trial medication compliance (for subjects treated with imiquimod)

Visit 10 – Only if Retreatment is required (Week 16, 56 days  $\pm$  3 days after Visit 6)

Visit 10 will include:

- Clinical assessment of neoplasia in the selected treatment area (biopsy if there is suspicion of SCC, BCC or other neoplasia)
- Dermatologic examination of selected treatment area including LSRs and AK count
- Reporting of (S)AEs (see [Table 2](#))
- Reporting of concomitant medication, treatments and procedures
- Urine pregnancy test for female subjects of childbearing potential
- Abbreviated physical examination

Visit 11 (Week 20  $\pm$  14 days)

Visit 11 will include:

- Clinical assessment of neoplasia in the selected treatment area (biopsy if there is suspicion of SCC, BCC or other neoplasia)
- Dermatologic examination of selected treatment area including AK count
- Reporting of (S)AEs (see [Table 3](#))
- Reporting of concomitant medication, treatments and procedures

Visit 12 (Month 12 ± 14 days)

Visit 12 will include:

- Clinical assessment of neoplasia in the selected treatment area (biopsy if there is suspicion of SCC, BCC or other neoplasia)
- Dermatologic examination of selected treatment area including AK count
- Reporting of (S)AEs (see [Table 3](#))
- Reporting of concomitant medication, treatments and procedures
- Abbreviated physical examination

Visit 13 (Month 18 ± 28 days)

Visit 13 will include:

- Clinical assessment of neoplasia in the selected treatment area (biopsy if there is suspicion of SCC, BCC or other neoplasia)
- Dermatologic examination of selected treatment area including AK count
- Reporting of (S)AEs (see [Table 3](#))
- Reporting of concomitant medication, treatments and procedures
- Abbreviated physical examination

Visit 14 (Month 24 ± 28 days)

Visit 14 will include:

- Clinical assessment of neoplasia in the selected treatment area (biopsy if there is suspicion of SCC, BCC or other neoplasia)
- Dermatologic examination of selected treatment area including AK count
- Reporting of (S)AEs (see [Table 3](#))
- Reporting of concomitant medication, treatments and procedures
- Abbreviated physical examination

Visit 15 (Month 30 ± 28 days)

Visit 15 will include:

- Clinical assessment of neoplasia in the selected treatment area (biopsy if there is suspicion of SCC, BCC or other neoplasia)
- Dermatologic examination of selected treatment area including AK count
- Reporting of (S)AEs (see [Table 3](#))
- Reporting of concomitant medication, treatments and procedures

- Abbreviated physical examination

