#### 10.7.5.1 Reporting of Adverse Events

Events reported by the subject or observed by the (sub)investigator and that fall into any of the categories below must be recorded on the adverse event page of the CRF:

Table 2: Adverse Event Reporting for Visits until Week 20

Adverse Event	Inside treatment area	Outside treatment area including non-cutaneous events
BCC/SCC	All BCC/SCCs should be recorded in the CRF and reported to LEO as SAEs.	All serious and non-serious BCC/SCCs should be recorded in the CRF.  Serious BCC/SCCs should be reported to LEO as SAEs.
Other AEs	All AEs and SAEs should be recorded in the CRF.  Serious AEs should be reported to LEO as SAEs.	All AEs and SAEs should be recorded in the CRF.  Serious AEs should be reported to LEO as SAEs.

Table 3: Adverse Event Reporting for Visits after Week 20

Adverse Event	Inside treatment area	Outside treatment area including non-cutaneous events
BCC/SCC	All BCC/SCCs should be recorded in the CRF and reported to LEO as SAEs.	All serious and non-serious BCC/SCCs should be recorded in the CRF.  Only serious BCC/SCCs related to the treatment should be reported to LEO as SAEs.
Other AEs	All AEs and SAEs should be recorded in the CRF.  Serious AEs should be reported to LEO as SAEs.	Only SAEs related to the treatment should be recorded in the CRF.  These should be reported to LEO as SAEs.

*Please note: Local Skin Responses which match the criteria in the LSR Grading Scale are to be reported as LSRs in the CRF and not as AEs even if they require treatment. Any treatment should be recorded on the Concomitant medication page of the CRF together with the most important LSR (e.g. swelling should be reported as swelling-LSR).*

Adverse events should be described in the following manner:

The **nature** of the event will be described in precise English medical terminology (i.e. not necessarily the exact words used by the subject). Whenever possible, a specific diagnosis should be stated (e.g. allergic contact dermatitis).

For adverse events the anatomical **location** of the adverse event must be part of the adverse event description and may be described as the ‘in the selected treatment area’, ‘within 5 cm of the selected treatment area’, ‘more than 5 cm from the selected treatment area’ (with further specification for BCC/SCCs) or ‘not applicable’.

The **intensity** of the event will be described in terms of mild, moderate or severe according to the investigator’s clinical judgement.

- 

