### **10.7.6 Serious adverse events**

#### **10.7.6.1 Reporting of Serious Adverse Events**

Any Serious Adverse Event (SAE), related or unrelated to the investigational product or any trial procedure after signature of the Informed Consent Form must be reported to LEO Pharma A/S on the (paper) **Serious Adverse Event Form – Clinical Trial** within **one calendar day, with the exception that:**

- After Week 20, non-related serious adverse events outside the treatment area should *not* be reported to LEO Pharma A/S (see [Table 2](#) and [Table 3](#))

---

An LSR classified as a SAE must be reported on the adverse event form in the CRF and reported to LEO Pharma A/S on the paper *Serious Adverse Event Form (SAE) – Clinical Trial*.

**Note:** Planned hospitalisation or planned prolonged hospitalisation do not fulfil the criteria for being an SAE. The elective nature of the event must be clearly documented in the subject's medical record.

SAEs must be reported on the adverse event form of the CRF book. Additionally reports must be made using the paper *Serious Adverse Event (SAE) Form – Clinical Trial*, supplied by LEO Pharma A/S. Apart from the assessment of the intensity, causal relationship to the investigational product(s) and/or trial procedures, the action taken and the outcome to date, this report must contain a comprehensive narrative description of the course of the event.

The completed LEO *Serious Adverse Event (SAE) Form – Clinical Trial* must be faxed or scanned and e-mailed Global Pharmacovigilance at LEO Pharma A/S:

LEO Pharma A/S Head Quarter  
Denmark, Global Pharmacovigilance  
[name]  
**Global Pharmacovigilance [contact]  
**E-mail:** [[contact]](mailto:[contact])

All other relevant reports of diagnostic procedures, hospital records, autopsy reports etc. must be included, as applicable or upon request from Global Pharmacovigilance.

The IRB(s)/IEC(s), regulatory authorities and concerned investigators will be notified of SAEs according to current regulation and local requirements.

All Suspected, Unexpected Serious Adverse Reactions (SUSARs) are subject to expedited reporting to regulatory authorities.

SAEs must be followed indefinitely until a final outcome has been established, i.e. the follow-up may continue beyond the end of the clinical trial.

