- Table 2-8 Annual incidence of SCC in the treatment area: per protocol analysis set [[Shell 6](#)]
- Table 2-9 Summary of SCC in the treatment area from baseline to end of trial: safety analysis set [[Shell 7](#)]
- Table 2-10 Summary of SCC in the treatment area from baseline to end of trial: per protocol analysis set [[Shell 7](#)]
- Table 2-11 Annual incidence of SCC and other neoplasia in the treatment area: safety analysis set [[Shell 6](#)]
- Table 2-12 Annual incidence of SCC and other neoplasia in the treatment area: per protocol analysis set [[Shell 6](#)]
- Table 2-13 Incidence of SCC in the treatment area by subgroups: safety analysis set [[Shell 8](#)]
- Table 2-14 Incidence of SCC in the treatment area by subgroups: per protocol analysis set [[Shell 8](#)]
- Table 2-15 Incidence of SCC and other neoplasia in the treatment area by subgroups: safety analysis set [[Shell 8](#)]
- Table 2-16 Incidence of SCC and other neoplasia in the treatment area by subgroups: per protocol analysis set [[Shell 8](#)]
- Table 2-17 Incidence of SCC and other neoplasia in the treatment area from week 20 to month 36: safety analysis set [[Shell 5](#)]

Trial ID: LP0041-63	Date: 28-AUG-2019	Version: Final 1.0 Page 19 of 32
---------------------	--------------------------	-------------------------------------

Table 2-18 Incidence of SCC and other neoplasia in the treatment area from week 20 to month 36: per protocol analysis set [[Shell 5](#)]

Table 2-19 Difference in the incidence of SCC in the treatment area: safety analysis set [[Shell 9](#)]

Table 2-20 Difference in the incidence of SCC in the treatment area: per protocol analysis set [[Shell 9](#)]

Table 2-21 Difference in the incidence of SCC and other neoplasia in the treatment area: safety analysis set [[Shell 9](#)]

Table 2-22 Difference in the incidence of SCC and other neoplasia in the treatment area: per protocol analysis set [[Shell 9](#)]

Adverse events

Table 2-23 Overall summary of adverse events from start of treatment to end of trial: safety analysis set

Table 2-24 Overall summary of adverse events from start of treatment to Week 20: safety analysis set

Table 2-25 Overall summary of adverse events from Week 20 to end of trial: safety analysis set

Table 2-26 Overall summary of adverse events by period: safety analysis set

Table 2-27 Adverse events from start of treatment to Week 20 by SOC: safety analysis set

Table 2-28 Adverse events by SOC: safety analysis set

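### The Week 20 visit is assigned the reduced adverse event rule meant for visits after Week 20, so non-serious events outside the treatment area may go unrecorded for 12 or 4 weeks, depending on clearance

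*Protocol*

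**What the plan says.** Protocol section 10.1.3 lists the tasks for each visit. For Visits 3 to 10 the adverse event line is "Reporting of (S)AEs (see [Table 2". For Visit 11 (Week 20 ± 14 days) and every later visit it is "Reporting of (S)AEs (see [Table 3".

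Section 10.7.5.1 holds the two tables. Their headings are "Table 2: Adverse Event Reporting for Visits until Week 20" and "Table 3: Adverse Event Reporting for Visits after Week 20".

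- Table 2 records every AE and SAE, inside and outside the treatment area.
- Table 3 still records everything inside the area. Outside it, a category that includes non-cutaneous events, the BCC/SCC row keeps full recording ("All serious and non-serious BCC/SCCs should be recorded in the CRF"). For all other events the rule is "Only SAEs related to the treatment should be recorded in the CRF".

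Section 10.7.6.1 requires every SAE, related or not, to be reported within one calendar day and entered on the CRF adverse event form. Its one exception is tied to time: "After Week 20, non-related serious adverse events outside the treatment area should *not* be reported to LEO Pharma A/S".

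Section 10.10.6.2 summarises AEs by period of start date, and the first period runs until Week 20. SAP Appendix I follows this with a series of tables such as Table 2-24, "Overall summary of adverse events from start of treatment to Week 20: safety analysis set".

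**The concern.** The visit list and the table headings disagree about the Week 20 visit. By its heading, Table 3 does not cover that visit, yet the visit list assigns it there.

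The disagreement matters because the rule reaches backwards. Under section 10.7.5 the subject is asked at each visit how they have been since the previous one, and the answer is filtered through whichever table applies. If Table 3 applies at Visit 11, it governs the whole interval back to the last visit, and all of that interval lies before Week 20 on the nominal schedule.

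The summaries to Week 20 would then claim a collection period that did not exist for one class of event. The length of the gap would also depend on whether the subject cleared at Week 8, which is an outcome of treatment. Section 8.3 says adverse events will be compared between the two treatments.

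**Working it through.** The documents give no figure for this interval, so there is none to reproduce. The check is arithmetic on the visit calendar.

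**Inputs (protocol sections 3.1, 10.1.3 and 10.7.1)**

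- Visit 6: Day 57 ± 3 days.
- Visit 10, retreated subjects only: 56 days after Visit 6, ± 3 days, so nominally Day 113.
- Visit 11: Week 20 ± 14 days, so nominally Day 1 + 140 = Day 141.
- Subjects cleared at Week 8 skip Visits 7 to 10 and go straight to Visit 11.

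**Interval governed by the Visit 11 rule**

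Interval = day of Visit 11 − day of the previous visit.

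- Cleared at Week 8: 141 − 57 = 84 days = 12 weeks, or 84/140 = 60% of the first 20 weeks. Window extremes: (141 − 14) − (57 + 3) = 67 days and (141 + 14) − (57 − 3) = 101 days, which is 9.6 to 14.4 weeks.
- Retreated: 141 − 113 = 28 days = 4 weeks, or 28/140 = 20%. Window extremes: 127 − (60 + 56 + 3) = 8 days and 155 − (54 + 56 − 3) = 48 days, which is 1.1 to 6.9 weeks.

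**What happens to each class of event with onset in that interval, if Table 3 is applied at Visit 11**

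| Event | Result |
|---|---|
| Any event inside the treatment area | Recorded |
| BCC/SCC outside the area | Recorded |
| Treatment-related SAE outside the area | Recorded |
| Unrelated SAE outside the area (not BCC/SCC), onset before Week 20 | Conflict: not recorded under Table 3, but reportable and entered on the CRF under 10.7.6.1 |
| Non-serious event outside the area (not BCC/SCC), related or not, including systemic events | Not recorded |

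**Dependence on clearance**

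Let p be the share of an arm that is clear at Week 8. Mean weeks of full collection outside the area = 8p + 16(1 − p). The documents give no expected Week 8 clearance by arm, so p is an assumption and a range is shown.

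| Assumed p, two arms | Mean weeks | Relative deficit in the better-clearing arm |
|---|---|---|
| Equal | Equal | 0% |
| 30% vs 35% | 13.6 vs 13.2 | 0.4/13.6 = 2.9% |
| 20% vs 40% | 14.4 vs 12.8 | 1.6/14.4 = 11.1% |
| 30% vs 50% | 13.6 vs 12.0 | 1.6/13.6 = 11.8% |

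These are deficits in collection time, not in event counts.

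**Outputs that rely on full collection to Week 20**

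SAP Tables 2-24, 2-27, 2-29, 2-31, 2-33, 2-35, 2-37, 2-40 and 2-49 include non-serious events. The SAE tables, 2-42 and 2-44, are touched only through the conflict between Table 3 and 10.7.6.1.

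**The case against.** The strongest reply is that this is a cross-reference conflict and not a demonstrated loss of data. The synopsis names section 10.7.5.1 as the place where reportable events are detailed for each phase, and by its headings Table 3 does not cover the Week 20 visit. A site that worked from the headings would lose nothing. That stands: the documents do not settle which text governs. It does not dispose of the point, because the visit list is the explicit instruction for that visit and sites may differ in which text they follow.

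A reader might also infer that unrelated serious events are lost, for example a hospitalisation at Week 12 in a subject cleared at Week 8. The documents do not support that. Section 10.7.6.1 keeps such an event reportable and on the CRF, so the passages conflict but loss is not certain.

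A reader might further infer that the better-clearing arm will look safer for this reason alone. That also goes too far. The size rests on an assumed clearance gap, and section 8.3 says imiquimod was chosen as the most comparable marketed field treatment in efficacy. With equal clearance the difference is zero. The arm that clears less also receives more second cycles, which affects its event count independently.

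The stakes are limited in two more ways. The synopsis places the primary AE analysis in the first 8 weeks, and Visits 3 to 6 all use Table 2. Planned dosing ends by Week 4 for one cycle or Week 12 for two, so at least 4 nominal weeks after dosing are fully collected in either case. Both points stand and lower the severity. They do not repair the summaries to Week 20, which section 10.10.6.2 and the SAP present without that 8-week restriction.

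**Conclusion.** The protocol contradicts itself on which adverse event rule applies at Week 20. Where sites follow the visit list, non-serious events outside the treatment area other than BCC/SCC, including treatment-related and systemic ones, go unrecorded for a nominal 12 weeks in subjects cleared at Week 8 and 4 weeks in retreated subjects. For unrelated SAEs outside the area before Week 20, the passages conflict.

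The 12 and 4 weeks follow from the visit schedule alone. The between-arm difference, from zero to about 12% of collection time, depends on assumed clearance rates.

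The primary SCC endpoint, the secondary neoplasia endpoint in the treatment field, the clearance endpoints, all events inside the area and the 8-week primary AE window are unaffected. The point should be fixed because it changes which safety data exist for a stated reporting period, but it does not threaten the main result.

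**What to change.** Change the Visit 11 reference in section 10.1.3 from Table 3 to Table 2. Define the switch between the tables by date of onset: Table 2 for onset up to and including Visit 11, Table 3 for onset after it. On the nominal schedule this reduces the 12- and 4-week gaps to zero.

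Use the same boundary in the headings of 10.7.5.1, the exception in 10.7.6.1, the periods in 10.10.6.2 and the SAP tables to Week 20. Because Visit 11 has a ± 14-day window, those texts should say whether Week 20 means the date of Visit 11 or a calendar day.

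The protocol plans completion of the last subject in Q2 2018 and the SAP is dated August 2019, so collection may already be over. In that case, establish from the CRF completion guidance which table sites applied at Visit 11. If it was Table 3, footnote the tables to Week 20 as incomplete for non-serious events outside the area after Week 8 (one cycle) or Week 16 (two cycles), and list the change in SAP section 7.5.6.

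The cost is one cross-reference, one line on onset date in the protocol and CRF guidance, and a few more non-serious events recorded at Visit 11. No visit or procedure is added.
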